8.3.2. Method of Detecting SAEs, ADEs, and SADEs

- Care will be taken not to introduce bias when detecting SAEs, ADEs, and/or SADEs. Open-ended and non-leading verbal questioning of the participant is the preferred method to inquire about SAE/ADE/SADE occurrence.

8.3.3. Follow-up of SAEs and SADEs

All SAEs/SADEs, will be followed until the event is resolved, stabilized, otherwise explained. Further information on follow-up procedures is given in [Appendix 2](#).

8.3.4. Regulatory Reporting Requirements for SAEs/SADEs

- Prompt notification by the investigator to the sponsor of an SAE/SADE is essential so that legal obligations and ethical responsibilities towards the safety of participants and the safety of a study intervention under clinical investigation are met.
- The sponsor has a legal responsibility to notify both the local regulatory authority and other regulatory agencies about the safety of a study intervention under clinical investigation. The sponsor will comply with country-specific regulatory requirements relating to safety reporting to the regulatory authority, Institutional Review Boards (IRB)/Independent Ethics Committees (IEC), and investigators.
- An investigator who receives an investigator safety report describing an SAE/SADE or other specific safety information (e.g., summary or listing of SAEs/SADEs) from the sponsor will review Investigator's Brochure and will notify the IRB/IEC, if appropriate according to local requirements.
- Investigator safety reports must be prepared for suspected unexpected serious adverse reactions (SUSAR) according to local regulatory requirements and sponsor policy and forwarded to investigators as necessary.
- The complaint including labelling failure must be logged, processed and reported under the requirements of the Regulation (EU) 2017/745 Medical Device Regulation (MDR) Article 80(2) and GSK Medical Device Complaint Management System in accordance with ISO 13485 procedural requirements for ELLIPTA Device. While for BREEZHALER, the data must be reported under the requirements of the Regulation (EU) 2017/745 Medical Device Regulation (MDR) Article 80(2). Further details on reporting are included in the study reference manual.

8.3.5. Cardiovascular and Death Events

For any cardiovascular events detailed in Section 10.2.3 and all deaths, whether or not they are considered SAEs, specific Cardiovascular (CV) and Death sections of the CRF will be required to be completed. These sections include questions regarding cardiovascular (including sudden cardiac death) and non-cardiovascular death.

The CV CRFs are presented as queries in response to reporting of certain CV MedDRA terms. The CV information should be recorded in the specific cardiovascular section of the CRF within one week of receipt of a CV Event data query prompting its completion.

The Death CRF is provided immediately after the occurrence or outcome of death is reported. Initial and follow-up reports regarding death must be completed within one week of when the death is reported.

8.3.6. Disease-Related Events and/or Disease-Related Outcomes Not Qualifying as SAEs

This section is not applicable

8.3.7. Adverse Events of Special Interest

This section is not applicable

8.3.8. Medical Device Deficiencies

Medical devices are being provided for use in this study. To fulfil regulatory reporting obligations worldwide, the investigator is responsible for the detection and documentation of events meeting the definitions of device deficiency that occur during the study with such devices.

The definition of a Medical Device Deficiency can be found in Section [10.7 Appendix 7](#) of the protocol.

8.3.8.1. Time Period for Detecting Medical Device Deficiencies

- Medical device deficiencies that result in an incident will be detected, documented, and reported during all periods of the study in which the medical device is used.
- If the investigator learns of any device deficiency at any time after a participant has been discharged from the study, and such device deficiency is considered reasonably related to a medical device provided for the study, the investigator will promptly notify the sponsor.
- The method of documenting Medical Device Incidents is provided in Section [10.6 Appendix 6](#) .

8.3.8.2. Follow-up of Medical Device Deficiencies

- Follow-up applies to all participants, including those who discontinue study intervention or the study.
- The investigator is responsible for ensuring that follow-up includes any supplemental investigations as indicated to elucidate the nature and/or causality of the deficiency.
- New or updated information will be recorded on the originally completed form with all changes signed and dated by the investigator.

8.3.8.3. Prompt Reporting of Medical Device Deficiencies to Sponsor

- Device deficiencies will be reported to the sponsor within 24 hours after the investigator determines that the event meets the protocol definition of a device deficiency.
- The Medical Device Deficiency Report Form will be sent to the sponsor electronically. If electronic is unavailable, then paper reporting should be utilized.
- The sponsor will be the contact for the receipt of device deficiency reports.

8.3.8.4. Regulatory Reporting Requirements for Medical Device Incidents

- The investigator will promptly report all deficiencies occurring with any medical device provided for use in the study in order for the sponsor to fulfil the legal responsibility to notify appropriate regulatory authorities and other entities about certain safety information relating to medical devices being used in clinical studies.
- The investigator, or responsible person according to local requirements (e.g., the head of the medical institution), will comply with the applicable local regulatory requirements relating to the reporting of device deficiencies to the IRB/IEC.

8.4. Pharmacokinetics

Pharmacokinetic parameters are not being evaluated in this study.

8.5. Genetics and/or Pharmacogenomics

Genetics are not being evaluated in this study.

8.6. Biomarkers

Biomarkers will not be evaluated in this study.

8.7. Immunogenicity Assessments

Immunogenicity assessments will not be performed

8.8. Health Economics OR Medical Resource Utilization and Health Economics

Health Economics/Medical Resource Utilization and Health Economics parameters are not evaluated in this study.

9. STATISTICAL CONSIDERATIONS**9.1. Statistical Hypotheses**

The primary purpose of this study is to assess the number of critical errors (defined as an error that is most likely to result in no or significantly reduced medication being inhaled) made by asthma participants, after they have read the patient information leaflet(s) (PIL) for each inhaler. This is a superiority study.

The primary estimand is the odds ratio between the ELLIPTA and BREEZHALER inhaler in participants with mild to moderate asthma who make at least one critical error while demonstrating use of the inhaler after reading the PIL(s) based on participants who were able to attempt to demonstrate the use of both inhalers.

The null hypothesis is that there is no difference in the proportion of participants who make at least one critical error on the ELLIPTA inhaler compared with the BREEZHALER inhaler:

$$H_0: P_{\text{ELLIPTA}} = P_{\text{BREEZHALER}}$$

The alternative hypothesis is that there is a difference in the proportion of participants who make at least one critical error on the ELLIPTA inhaler compared with the BREEZHALER inhaler:

$$H_1: P_{\text{ELLIPTA}} \neq P_{\text{BREEZHALER}}$$

This comparison will be tested at the two-sided 5% significance level.

9.2. Sample Size Determination

A total of 114 participants will be randomly assigned to study intervention such that approximately 114 evaluable participants complete the study.

The sample size for a 2x2 crossover study is based on the formula presented by [Chow](#), 2008 and [Kung-Jong](#), 2016. To calculate the conditional odds ratio (via McNemar's) the proportion of participants who have discordant pairs (those who had at least one critical error in one inhaler but not the other) was determined based on expert advice. A panel of 5 experts was convened to consider the evidence from previous studies of similar design [[van der Palen](#), 2016; [van der Palen](#), 2018] and with consideration given to observational studies in the literature [[Khassawneh](#), 2008; [Melani](#), 2011; [Arora](#), 2014; [Chorão](#), 2014; [Takaku](#), 2017; [Ocakli](#), 2018]. A consensus view of the likely error rates that would be observed with the ELLIPTA and BREEZHALER devices was subsequently reached.

A consensus was reached that the proportion of participants who make a critical error in the ELLIPTA inhaler and not on the BREEZHALER inhaler would be 6% and the proportion of patients who make a critical error in the BREEZHALER inhaler and not on the ELLIPTA inhaler would be 20%.

Based on the discordant proportions, an odds ratio of 0.3 was calculated and a standard deviation on the log odds ratio scale of 2.785 was calculated based on GSK study 200301 [[van der Palen](#), 2016]. Based on these estimates and a two-sided Type I error rate of 5%, a total of 114 participants are required to provide 90% power. No withdrawals are expected based on previous similarly designed studies. No correlation between periods is assumed and no carry over effect is assumed based on previous evidence [[van der Palen](#), 2013]. Moreover, both inhalers will contain placebo and participants may have up to a 30-minute break after demonstrating the first inhaler.

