4.2.2. Main analytical approach

Comparisons made between the ELLIPTA and BREEZHALER inhaler will be based on those who fall in the S₀₀ stratum. For the full definition of the primary estimand, see section 1.1.

The comparison of ELLIPTA with BREEZHALER will be summarized by an odds ratio. The proportion of participants who make at least one critical error in each inhaler will be analysed using an exact conditional logistic regression model with participant as fixed strata with inhaler, and period as fixed effects. To account for very small or zero frequency counts, an exact test has been specified. In case of period effects, period has been included in the model as a fixed effect (Mehta, et al., 1995). The odds ratio of ELLIPTA relative to BREEZHALER together with the 95% confidence interval and two-sided p-value will also be presented.

Superiority will be declared based on a significance level at the two-sided 5% level.

Residual vs. Fitted plots will be generated to help assess the constant variance assumption. Deviance and Pearson goodness of fit statistics from the model will be examined to help assess the null hypothesis that the model is an adequate fit to the data.

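### The stated 90% power with 114 participants does not follow from the plan's own 6%/20% discordance; the planned primary test has about 75% to 80%

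*Protocol*

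**What the plan says.** Protocol 9.2 and SAP 5 carry the same sample size text. An expert panel set the proportion making a critical error on ELLIPTA only at 6%, and on BREEZHALER only at 20%. The effect size follows: "Based on the discordant proportions, an odds ratio of 0.3 was calculated". The variability has a different source: "a standard deviation on the log odds ratio scale of 2.785 was calculated based on GSK study 200301". No withdrawals are allowed for, and the conclusion is that "a total of 114 participants are required to provide 90% power".

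Protocol 9.1 sets the error rate: "This comparison will be tested at the two-sided 5% significance level". The primary analysis in SAP 4.2.2 (also Protocol 9.4.1) is an "exact conditional logistic regression model with participant as fixed strata with inhaler, and period as fixed effects".

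**The concern.** The target is a conditional odds ratio of the McNemar type. For that quantity the two discordant proportions give the odds ratio (their ratio) and also its large-sample variance (the sum of their reciprocals). Once 6% and 20% are assumed, no free standard deviation is left to import. Taking the effect from one set of discordant proportions and the variance from somewhere else gives a sample size that belongs to neither.

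The sample size formula also takes no account of the test. That test is exact, hence conservative, and it conditions on period as well as participant; both cost power.

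At stake is the probability of missing a true effect of the assumed size. A reader told that it is 10% will read more into a non-significant result than the design supports.

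**Working it through.** **Inputs.** From Protocol 9.2: ELLIPTA-only 0.06, BREEZHALER-only 0.20, odds ratio 0.3, SD 2.785, N = 114, target power 90%, no withdrawals. From Protocol 9.1: two-sided 5%. Not in the documents and assumed here: equal sequences (57/57) and no true period effect.

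**1. Reproducing 114.** n per sequence = (z₀.₉₇₅ + z₀.₉₀)² × SD² / (ln OR)² = (1.960 + 1.282)² × 2.785² / (ln 0.3)² = 10.507 × 7.756 / 1.4496 = 56.2. Rounded up to 57 and doubled, this is 114, with power 90.4%. The multiplication is right for those inputs.

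**2. The variance that 6%/20% implies.** Per participant, Var(log OR) = 1/0.06 + 1/0.20 = 21.67 (SD 4.65). Step 1 amounts to 2 × 2.785² = 15.51 per participant (SD 3.94). The shortfall is 1 − 15.51/21.67 = 28%. On the per-sequence convention of step 1, 6%/20% gives an SD of √(21.67/2) = 3.29, not 2.785, and a total of 158.

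In reverse, SD 2.785 with odds ratio 0.3 requires BREEZHALER-only = (1/0.3 + 1)/15.51 = 27.9% and ELLIPTA-only = 0.3 × 27.9% = 8.4%. That is about 36% discordant in total, against the panel's 26%.

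**3. Large-sample power at N = 114.**
- Wald test on the log odds ratio: SE = √(21.67/114) = 0.436; 1.204/0.436 = 2.762; Φ(2.762 − 1.960) = 78.9%.
- McNemar, closed form, with total discordance 0.26 and difference 0.14: Φ[(0.14√114 − 1.960√0.26)/√(0.26 − 0.14²)] = Φ(1.01) = 84.4%. The same formula needs 136 participants for 90%.

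**4. The planned test.** Given participant, only discordant participants contribute, and each has the single error in period 1 or period 2. With inhaler and period in the model, conditioning on the period total leaves a hypergeometric test of sequence by period of the error. Power follows by enumerating the discordant counts in each sequence.

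| Test at N = 114, 6%/20%, two-sided 5% | Power | N for 90% |
|---|---|---|
| Planned exact test with period, doubled tail | 75.4% | about 158 (89.9% at 156, 90.3% at 158) |
| Planned exact test with period, probability-ordered | 79.6% | about 148 (90.3%) |
| Planned test with period, mid-p | 83.1% | about 140 (90.7%) |
| Exact McNemar, no period | 81.1% | 143 |
| McNemar, mid-p | 85.2% | 131 |
| Uncorrected McNemar, enumerated | 86.8% | 128 |

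Only a one-sided 5% test comes close to the stated figure (exact McNemar 89.4%), and the plan is two-sided.

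**5. Where 90% does hold with 114.** Keeping ELLIPTA-only at 6%, the planned test has 88.6% (doubled) or 91.0% (probability-ordered) power at BREEZHALER-only 23%, and 91.5% or 93.4% at 24%. The corresponding odds ratios are 0.06/0.23 = 0.26 and 0.06/0.24 = 0.25.

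**The case against.** The strongest reply is that 114 is computed correctly. The text rests it on all the stated estimates, which include the SD, and with odds ratio 0.3 and SD 2.785 the result is 114. The SD comes from a named study, whereas 6%/20% is expert consensus. If the SD is the better input, discordance is about 8.4%/27.9%, and the planned test then has about 91% to 93% power at 114. On this view the documents show that two inputs conflict but not which is wrong.

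That is right about the multiplication, and the derivation of 2.785 cannot be checked from the documents. It does not rescue the statement. The sections name 6% and 20% as the assumptions and derive the odds ratio from them; at those values the power is not 90% under any two-sided test examined. Defending the SD means giving up the stated discordance, so the text has to change either way.

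Two smaller points stand. The 75% to 80% range depends on the sequence split, the absence of a period effect and the p-value convention, so these must be stated with it. The 84% for McNemar is a closed-form approximation and should be labelled as such. It is also true that the type I error, the estimate and its confidence interval are unaffected.

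**Conclusion.** The concern holds. With 114 participants and the plan's 6%/20%, the planned primary test has 75.4% (doubled tail) to 79.6% (probability-ordered) power, assuming 57 per sequence and no true period effect. The type II error is about 20% to 25%, at least twice the stated 10%. The conclusion does not hang on those assumptions: dropping period gives 81.1% for exact McNemar, and the most favourable two-sided version gives about 87%. The cause is a variance about 28% too small for the stated discordance, together with a formula that does not reflect the exact, period-adjusted test. The 28% relies on the reading of the formula that reproduces 114, because the cited formula itself is not in the documents.

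**What to change.** In Protocol 9.2 and SAP 5, drop the SD of 2.785 and restate the power. With 114 participants, 6%/20% discordance, equal sequences and no period effect, the planned exact conditional logistic test at two-sided 5% has about 75% to 80% power. For comparison, McNemar's large-sample formula gives 84%. Name the two-sided p-value convention in SAP 4.2.2, so that one figure can replace the range.

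Equivalently, keep the 90% but state where it applies: BREEZHALER-only discordance of about 23% to 24% with ELLIPTA-only at 6% (odds ratio about 0.25 to 0.26). If the sponsor prefers to stand by the SD, the stated discordance has to become about 8.4%/27.9%, with a reason for departing from the panel.

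The cost is a text change in the two sample size sections, a line in SAP 4.2.2 and a less favourable stated figure. No extra enrolment is needed to make the correction. Holding 90% at 6%/20% would take about 148 to 158 participants.

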9.3. Analysis Sets

For the purposes of analysis, the following analysis data sets are defined:

Participant Analysis Set	Description
Screened	All participants screened and Signed ICF
Randomized	All participants randomized
Performance Evaluable	All participants who complete reading of the PIL(s) and attempt demonstration on both inhalers.
Safety	All randomized participants who complete (whether successful or unsuccessful) at least one inhalation with any study inhaler

9.4. Statistical Analyses

The statistical analysis plan will be finalized prior to data base lock (DBL) and it will include a more technical and detailed description of the statistical analyses described in this section. This section is a summary of the planned statistical analyses of the most important endpoints including primary and key secondary endpoints.

9.4.1. Primary Endpoint

Objectives	Statistical Analysis Methods
Primary	
Primary estimand
 
The proportion of participants who make at least one critical error in each inhaler (ELLIPTA or BREEZHALER) after reading the section on inhaler use in the PIL(s) assessed on the Day/Visit 1.
 
The primary treatment effect to be estimated will be the comparison of the ELLIPTA inhaler to the BREEZHALER inhaler.
 
The population will be participants with mild to moderate asthma who attempt demonstration of both inhalers.
 
The population-summary measure is an odds ratio.
 
The intercurrent event is participants who do not attempt demonstration of the inhaler (ELLIPTA or BREEZHALER). A principal stratum strategy will be used to address the intercurrent event. Participants will fall into exactly one of the following four strata:
 
 1. S_{00}: Stratum of randomized participants who attempt inhaler demonstration (ELLIPTA and BREEZHALER) independent of period.

Objectives	Statistical Analysis Methods
	
2. S_{01}: Stratum of randomized participants who attempt the demonstration of the BREEZHALER inhaler and do not attempt demonstration of the ELLIPTA inhaler independent of period.
 
3. S_{10}: Stratum of randomized participants who attempt the demonstration of the ELLIPTA inhaler and do not complete demonstration of the BREEZHALER inhaler independent of period.
 
4. S_{11}: Stratum of randomized participants who do not attempt inhaler demonstration (ELLIPTA and BREEZHALER) independent of period.
 
The estimated treatment effect will be based on participants who fall in the S_{00} strata.
 
The comparison of ELLIPTA with BREEZHALER will be summarized by an odds ratio. The proportion of participants who make at least one critical error in each inhaler will be analysed using an exact conditional logistic regression model with participant as fixed strata with inhaler, and period as fixed effects. The odds ratio of ELLIPTA relative to BREEZHALER together with the 95% confidence interval and two-sided p-value will also be presented.
 
Superiority will be declared based on a significance level at the two-sided 5% level.
 
Sensitivity analysis
 
A sensitivity analysis will be performed using a generalised mixed effects model with a binomial family and log link with a random effect for participant ID and inhaler, period, age and sex as fixed effects. An unstructured variance-covariance matrix will be used.

9.4.2. Secondary Endpoint(s)

Estimands for the secondary variables will use the same inhaler comparison, population and strategy for the intercurrent event as for the primary estimand. This means the estimated treatment effect comparing the ELLIPTA inhaler to the BREEZHALER inhaler will be based on the stratum of participants who were able to attempt demonstration on both inhalers. All comparisons will be made at the two-sided 5% significance level.

Objectives	Statistical analysis methods
To compare the proportion of participants who still make at least one critical error after	
Participants who still make at least one critical error after receiving further instruction (up to 3) from the HCP.
 
Participants receive further instruction if an error was made after reading the PIL.

Objectives	Statistical analysis methods

receiving further instruction from the Healthcare Professional (HCP) for ELLIPTA and BREEZHALER inhalers
	
 • Variable: participants making at least one critical error after the a) first instruction from the HCP (attempt 2), b) the second instruction from HCP (attempt 3) and c) third instruction from the HCP (attempt 4). • Population-summary measure: The odds ratio of participants making at least one critical error between the ELLIPTA and BREEZHALER inhalers. 
a) The denominator will include all participants who fall in the S₀₀ stratum. Participants who do not receive the first HCP instruction are assumed to have zero critical errors.
 
b) The denominator for those that require a second further instruction will include all participants who fall in the S₀₀ stratum. Participants who do not receive the second HCP instruction are assumed to have zero critical errors.
 
c) The denominator for those that require a third further instruction will include all participants who fall in the S₀₀ stratum. Participants who do not receive the third HCP instruction are assumed to have zero critical errors.
 
The analysis method will be the same as for the primary endpoint.
 
Note: This model will only be fitted if there is sufficient data, otherwise summary statistics will be presented.


To compare the proportion of overall errors made by participants after reading the inhaler use sections of the PIL, and if necessary, with additional instruction from the HCP for ELLIPTA and BREEZHALER inhalers
	
 • Participants who make at least one overall error after reading the PIL(s) (Attempt 1). • Variable: participants who make at least one overall error after reading the PIL. • Population-summary measure: The odds ratio between the ELLIPTA and BREEZHALER inhalers. 
The analysis method will be the same as for the primary endpoint.
 
This will be repeated for the participants who still make at least one overall error after receiving further instruction (up to 3) from the HCP. Participants receive further instruction if an error was made after reading the PIL.

Objectives	Statistical analysis methods
	
 • Variable: participants who make at least one overall error after the a) first instruction from the HCP (attempt 2), b) the second instruction from HCP (attempt 3) and c) third instruction from the HCP (attempt 4). • Population-summary measure: The odds ratio of participants making at least one overall error. 
a) The denominator will include all participants who fall in the S₀₀ stratum. Participants who do not receive the first instruction by the HCP are assumed to have zero overall errors.
 
b) The denominator for those that require a second further instruction will include all participants who fall in the S₀₀ stratum. Participants who do not receive the second HCP instruction are assumed to have zero overall errors.
 
c) The denominator for those that require a third further instruction will include all participants who fall in the S₀₀ stratum. Participants who do not receive the third HCP instruction are assumed to have zero overall errors.
 
Note: the model will only be fitted for the endpoints where further instruction is required provided there is sufficient data, otherwise summary statistics will be presented.

To summarize the number of errors (critical and overall) made on each inhaler, with or without further HCP instruction.	
Number of errors (critical and overall) made after reading the PIL(s), and, if necessary, after receiving further instruction from the HCP.
 
 • Variable: Critical and overall errors made with or without further HCP instruction. • Population-summary measure: The number of critical errors and overall errors made will be presented for each inhaler by instruction (0, 1, 2, 3).
To compare the proportion of participants that require further instruction from the HCP to demonstrate correct inhaler use for ELLIPTA and BREEZHALER inhalers	
Requiring further instruction from the HCP to demonstrate correct inhaler use:
 
 • Variable: participants who do or do not require further instruction from the HCP. • Population-summary measure: The number and percentage of participants who require further instruction from the HCP will be summarized. 
A McNemar's test will be performed comparing the proportion of requiring further instruction on the ELLIPTA

Objectives	Statistical analysis methods
	inhaler vs. requiring further instruction on the BREEZHALER inhaler.
To compare the Training/Teaching Time required to demonstrate correct inhaler use for ELLIPTA and BREEZHALER inhalers	
The amount of time taken to demonstrate inhaler use without HCP intervention (T1).
 
 • Variable: time taken to demonstrate inhaler use without HCP intervention (T1). • Population-summary measure: Median time to demonstrate inhaler use. 
The median time will be taken from the Kaplan-Meier model. Additionally, the mean (SD), median, minimum and maximum will also be presented for participants who demonstrate correct inhaler use.
 
Participants who fail to demonstrate the correct use will be censored at the end of T1.
 
The amount of time taken to be given instruction by the HCP (up to 3 times) on use of the inhaler and to demonstrate inhaler use (T2).
 
 • Variable: time taken to be given instruction by the HCP (up to 3 times) on use of the inhaler and demonstrate inhaler use (T2). • Population-summary measure: Median time to demonstrate inhaler use. 
The median time will be taken from the Kaplan-Meier model. Additionally, the mean (SD), median, minimum and maximum will also be presented for participants who demonstrate correct inhaler use.
 
 • Those who demonstrate correct use after reading the PIL (and therefore do not require further instruction) will be considered as demonstrating correct use at T2 and time taken to demonstrate correct use will equal to 0 minutes. The total amount of time taken to demonstrate correct inhaler use until correct demonstration is observed (T1+T2). Variable: total time taken to demonstrate inhaler use (T1+T2). • Population-summary measure: Median time and to demonstrate inhaler use. 
The median time will be taken from the Kaplan-Meier model. Additionally, the mean (SD), median, minimum and maximum will also be presented for participants who demonstrate correct inhaler use.

To compare ease-of-use for ELLIPTA and	
 • Ease-of-use preference from questionnaire. This will be grouped as easy [REDACTED] or difficult [REDACTED]

Objectives	Statistical analysis methods
BREEZHALER inhalers	
CCI that is, how the ease of use is rated by the participant.
 
 ○ Variable: ease of use rating. ○ Population-summary measure: The number and percentage of participants who rate the inhaler easy to use. To test whether the ease of use was easy or difficult, a McNemar's test will be performed. 
The population-measure summary defined above will be the same way for the following variables as indicated by participants' ease of use:
 
 • Telling how many doses are left in inhaler • Learning how to use the inhaler • Handling the inhaler • Preparing the inhaler • Holding the inhaler while using it
To summarise ease-of-use for ELLIPTA and BREEZHALER inhalers	
 • Ease-of-use preference from questionnaire, that is, how the ease of use is rated CCI 
CCI
 
 ○ Variable: ease of use rating. ○ Population-summary measure: The number and percentage of participants who rate the inhaler for each category. 
The population-measure summary defined above will be the same way for the following variables as indicated by participants' ease of use:
 
 • Telling how many doses are left in inhaler • Learning how to use the inhaler • Handling the inhaler • Preparing the inhaler • Holding the inhaler while using it
To compare the willingness to continue with the ELLIPTA and/or BREEZHALER inhaler	
Willingness to continue with the inhaler using a VAS between 0 CCI to 100 CCI
 
 • Variable: Willingness to continue with the inhaler. • Population summary measure: The mean and standard deviation for willingness to continue with the inhaler will be presented for each inhaler and a comparison made between the inhalers (ELLIPTA vs. BREEZHALER). 
The mean (SD), minimum and maximum will be presented. A paired t-test will be performed comparing the mean

Objectives	Statistical analysis methods
	willingness to continue with the ELLIPTA inhaler vs. the mean willingness to continue with the BREEZHALER inhaler.
To compare preference attributes for ELLIPTA and BREEZHALER inhalers	
Participants who expressed a preference on attributes from the preference questionnaire.
 
 • Variable: preferred inhaler, overall. • Population-summary measure: The number and percentage of participants who prefer the respective inhaler overall (ELLIPTA, BREEZHALER or no preference). A comparison will be made between the inhalers (ELLIPTA vs. BREEZHALER) using Prescott's test, where participants who select "no preference" included as uninformative. 
The population-summary measure defined above will be the same for the following variables as indicated by the participant's preference:
 
 • Preference based on the number of steps to take the medication. • Preference based on the time needed to take the medication. • Preference based on how easy the inhaler is to use. • Preference based on the size of the inhaler. • Preference based on the comfort of the mouthpiece. • Preference based on the ease of opening the inhaler.

